Dose proportionality will also be examined for maribavir PK parameters for the Japanese subjects. Dose proportionality will be assessed for C_{max} and AUC (AUC_{last} and AUC_{0-inf}) using the power model. The power model assumes a linear relationship between the natural log transformed parameter and the natural log transformed dose.

$$\ln(\text{Parameter}) = \alpha + \beta \times \ln(\text{Dose}) + \text{Random error}$$

Where α is the intercept, β is the slope, and Random error is a random residual error. Dose proportionality will be assessed by estimating mean slope with the corresponding two-sided 90% CI from the power model. The fold increase in PK parameters and associated 90% CI when doubling the dose will be presented. [REDACTED]

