#### 2.1.2 Secondary Objectives

- To assess the dose proportionality of maribavir PK following single oral doses of 200 mg, 400 mg, and 800 mg of maribavir in healthy, adult subjects of Japanese descent.
- To assess the safety and tolerability of single oral doses of 200 mg, 400 mg, and 800 mg of maribavir in healthy, adult subjects of Japanese descent.
- To evaluate the safety and tolerability of a single 400 mg oral dose of maribavir in matched, healthy, adult, non-Hispanic, Caucasian subjects.

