#### **Treatment Period:**

The non-Hispanic, Caucasian subjects will have one Treatment Period. The Japanese subjects will have Treatment Periods 1, 2, and 3.

- In Treatment Period 1, all study subjects (both Japanese and Caucasian) will receive maribavir as a single 400 mg oral dose.
- Depending upon the randomization assignment on Day 1 of treatment period 2, all subjects of Japanese descent will be dosed in a crossover fashion in Treatment Periods 2 and 3. They will receive a single oral dose of either 200 mg followed by 800 mg maribavir or a single oral dose of 800 mg followed by 200 mg maribavir.

The study design flow chart is presented in [Figure 1](#).

Figure 1 Study Design Flow Chart

\*Washout period of 72 to 73 hours after treatment on Day 1.

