#### Dose proportionality

Dose proportionality will also be examined for maribavir PK parameters for the Japanese subjects. Dose proportionality will be assessed for  $C_{max}$  and AUC ( $AUC_{last}$  and  $AUC_{0-inf}$ ) using the power model. The power model assumes a linear relationship between the natural log transformed PK parameter and the natural log transformed dose.

$\ln(\text{PK Parameter}) = \alpha + \beta \times \ln(\text{Dose}) + \text{Random error}$

where  $\alpha$  is the intercept,  $\beta$  is the slope, and Random error is a random residual error. Dose proportionality will be assessed by estimating mean slope with the corresponding two-sided 90% CI from the power model. Dose proportionality is concluded when the 90% CIs of the slope  $\beta$  lie entirely within  $(1 + \ln(0.8)/\ln(r), 1 + \ln(1.25)/\ln(r))$ , where  $r$  is a ratio that describes the dose range and is defined as (highest dose/lowest dose). The fold increase in PK parameters and associated 90% CI when doubling the dose will be presented.

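### The dose-proportionality slope gives the 400 mg results zero weight and has no linearity check, so proportionality over three doses can be concluded with 400 mg 20-30% off the line

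*SAP*

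**What the plan says.** The secondary objective in SAP 2.1.2 names three doses: "To assess the dose proportionality of maribavir PK following single oral doses of 200 mg, 400 mg, and 800 mg", in the Japanese cohort. The method in SAP 8.3 is a straight line on the log-log scale: "The power model assumes a linear relationship between the natural log transformed PK parameter and the natural log transformed dose". The model has an intercept, a slope and one error term, described as "Random error is a random residual error"; no subject, period or curvature term is written.

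Protocol 8.7.1.1 stops at estimation: "Dose proportionality will be assessed by estimating mean slope with the corresponding two-sided 90% CI from the power model". SAP 8.3 adds the decision: "Dose proportionality is concluded when the 90% CIs of the slope" fall wholly within limits set by r, the highest dose divided by the lowest. The fold increase per doubling is reported as well.

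The other model-based comparisons in SAP 8.3 are all Japanese versus Caucasian, and SAP 10 plans no further analyses.

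On the order of doses, SAP 3.1 states: "In Treatment Period 1, all study subjects (both Japanese and Caucasian) will receive maribavir as a single 400 mg oral dose". Only 200 and 800 mg are randomised, over Periods 2 and 3 (SAP 3.2).

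**The concern.** The objective covers two dose steps, 200 to 400 mg and 400 to 800 mg, but the rule tests one number. With these three doses that number compares the two ends. A more-than-proportional first step and a less-than-proportional second step can cancel, leaving a slope near 1 and a reported increase near 2.0-fold per doubling that holds for neither step.

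400 mg is the dose that matters most here. Protocol 3.1 gives 400 mg BID as the Phase 3 regimen, the dose-normalised parameters are scaled to 400 mg, and Protocol 2.1 says the results will guide dose selection in Japanese patients. A conclusion worded for all three doses would then claim more than the test had examined.

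**Working it through.** **Inputs.** Doses 200, 400 and 800 mg (SAP 2.1.2); n = 12 Japanese subjects, each planned to take all three (SAP 3.1); two-sided 90% CI and the limits formula (SAP 8.3). The documents give no CV and no power for this objective, so there is no stated figure to reproduce. Within-subject CV 10-20% and between-subject CV 10-40% are assumptions.

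**Limits.** r = 800/200 = 4. Lower: 1 + ln(0.8)/ln(4) = 0.839. Upper: 1 + ln(1.25)/ln(4) = 1.161. Per doubling this is 2^0.839 = 1.79-fold to 2^1.161 = 2.24-fold. A slope of exactly 1 leaves room for a CI half-width of 0.161.

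**Weights.** The mean of ln 200, ln 400 and ln 800 is ln 400, so the centred doses are -ln 2, 0 and +ln 2. Each weight is the centred dose divided by 2(ln 2)^2 = 0.961, giving -0.721, 0 and +0.721. With complete data the slope is ln(geometric mean at 800 / geometric mean at 200) / ln 4, with or without a subject term.

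**What 400 mg does affect.** If 400 mg lies off the line by a factor g, the residual sum of squares rises by n(2/3)(ln g)^2. For g = 1.25 this is 12 × 0.667 × 0.0498 = 0.398. With a subject term (23 df) the residual variance rises by 0.398/23 = 0.0173. The slope's sum of squares is 12 × 0.961 = 11.53. At within-subject CV 10% (log-scale variance ln(1.01) = 0.00995), the half-width is 1.714 × √(0.00995 + 0.0173)/√11.53 = 0.083, against 0.050 with no departure. It still fits within 0.161.

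**What g = 1.25 means.** The steps are 2 × 1.25 = 2.5-fold and 2/1.25 = 1.6-fold, both outside 1.79-2.24, and the expected slope is exactly 1.00. On the log scale 25% above the line equals 20% below it, because ln 1.25 = -ln 0.8.

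**Simulation.** Percentage of trials concluding proportionality, true end-to-end slope 1, within-subject CV 10/15/20%:

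| 400 mg relative to the line | Subject term in model | Model as written, between-subject CV 30% |
|---|---|---|
| On the line | 100/94/70 | 38/20/9 |
| 25% above (or 20% below) | 99/82/52 | 27/13/5 |
| 30% below | 85/51/24 | 12/5/2 |

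Runs differ by about one point (51 or 52, 12 or 13). At 30% below the line the steps are 1.40- and 2.86-fold. With a subject term, 40% below the line passes in 12/5/2% and a two-fold departure never passes.

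The model as written depends strongly on between-subject CV. For 20% below the line at within-subject CV 10%, it concludes proportionality in 98/76/27/6% at between-subject CV 10/20/30/40%.

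**Contrast with the top dose.** A 20% shortfall at 800 mg moves the slope to 1 + ln(0.8)/ln(4) = 0.839, on the limit. It passes in only 2-5% of trials at within-subject CV 10-20%.

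**Period.** Every 400 mg value comes from Period 1, so the contrast of 400 mg with the geometric mean of 200 and 800 mg is also the contrast of Period 1 with Periods 2 and 3.

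**The case against.** The decision uses the "corresponding two-sided 90% CI from the power model", not the point estimate. A reader might infer from the zero weight that the rule ignores 400 mg altogether. It does not: a departure widens the CI, and a large one makes the rule fail. The zero weight also needs complete data. Protocol 4.5 does not replace subjects lost in Periods 2 or 3; if 2 of 12 miss 800 mg, the 400 mg weight becomes about 0.05 without a subject term or 0.07 with one.

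A reader might take the 99/82/52% as rates for the SAP's model. They are not, since SAP 8.3 writes no subject term. The model as written passes less often at high between-subject CV, but because its CI is wide, not because it detects curvature: it also passes only 38/20/9% when proportionality is true.

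A reader might also infer that a departure would go unseen. SAP 8.2 reports dose-normalised geometric means with 95% CIs by dose group, SAP 8.3 compares each Japanese dose with the same Caucasian 400 mg reference, and CPAP Table 8 plans dose-normalised box plots across doses. A departure would show there, although none of these outputs enters the conclusion.

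Nothing in the documents predicts a departure at 400 mg. Protocol 1.2.3 and 3.1 report proportionality up to 900 mg in earlier studies, together with time-independent PK and a half-life of 5-7 hours. The 72-hour washout exceeds ten half-lives (72/7 = 10.3). Protocol 3.1 fixes 400 mg in Period 1 on purpose, to protect the cohort comparison. A Period 1 effect cannot bias the slope when data are complete, because the slope then rests on the two randomised doses.

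Finally, making step-ratio CIs within 0.80-1.25 a condition would be costly: at within-subject CV 20%, true proportionality would be concluded in about 45-47% of trials instead of 70%. It would also bring the Period 1 aliasing into the decision. These points stand, and they argue for supportive reporting. They do not supply the missing linearity check.

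**Conclusion.** The point holds in a limited form. With complete data the slope is an 800 versus 200 mg comparison, and 400 mg acts only through the CI width. The rule can therefore conclude proportionality over three doses with 400 mg roughly 20-30% off the line. The algebra is exact. The frequencies depend on the CVs and on whether a subject term is fitted, neither of which the documents settle. The documents do not support saying that exposure at 400 mg is off the line, that the report would conceal it if it were, or that the slope rule must be replaced. This is a cheap improvement to a secondary analysis, and it makes the conclusion match what was tested.

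**What to change.** Keep the slope rule in SAP 8.3 unchanged and add the following:

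- Within-Japanese dose-normalised geometric mean ratios, 400/200 and 800/400 mg, and the curvature contrast (400 mg versus the geometric mean of 200 and 800 mg). Give 90% CIs from a model with dose as a factor and a subject effect, and label them supportive, not an equivalence gate.
- A wording rule: if the slope criterion is met but the curvature CI excludes 1, state proportionality between 200 and 800 mg only.
- A note that any contrast involving 400 mg also carries any Period 1 versus Periods 2/3 difference.

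The contrast is precise enough to be useful. Its log-scale half-width is 1.717 × s × √(1.5/12) on 22 df, where s is the within-subject log-scale SD. At CV 20% (s = 0.198) this is 0.120, well below ln 1.25 = 0.223.

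The cost is one extra table from parameters already specified in CPAP Tables 4 and 5. A 90% CI excludes 1 by chance in about 10% of truly linear cases for each parameter, and the conclusion would then be narrower than necessary.

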## 9. PHARMACODYNAMIC ANALYSIS

Not applicable.

## 10. OTHER ANALYSES

No other analyses are planned for this study.

**11. INTERIM ANALYSIS/ DATA MONITORING (REVIEW) COMMITTEE**

Not applicable.

## 12. DATA HANDLING CONVENTIONS

### 12.1 General Data Reporting Conventions

Continuous variables will be summarized using the following descriptive statistics: n, mean, median, SD, minimum, and maximum. Categorical and count variables will be summarized by the number and the percent of subjects (n, %) in each category.

The following rules will be applied for decimal places and rounding:

1. For measures of median and mean, 1 decimal place beyond those used for the measurement will be reported.
2. For measures of SD and standard error of the mean, 2 decimal places, beyond those used for the measurement, will be reported.
3. For measures of minimum and maximum values, the same number of decimal places will be used as those used for the measurement.
4.  $\geq 5$  will be rounded up away from zero, whereas  $< 5$  will be rounded down toward zero to account for rounding of negative numbers.
5. For p-values, 3 decimal places will be used.
6. P-values that would round to 0.000 will be displayed as  $< 0.001$ .
7. BMI should be rounded to 1 decimal place for reporting.
8. Averaged lab results (e.g. diastolic/systolic blood pressure and pulse [when taken in triplicate]) should be rounded to 1 decimal place for reporting.
9. For PK Related shells, display should be to the defined level of significant digits.

### 12.2 Repeated or Unscheduled Assessments of Safety Parameters

If a subject has repeated assessments before the start of investigational product, then the results from the final assessment made prior to the start of investigational product will be used as baseline. If end of study assessments are repeated or unscheduled, the last post-baseline assessment will be used as the end of study assessment for generating descriptive statistics. If there are repeated assessments at other post-baseline timepoints, the assessment from scheduled visit will be considered for summarizing data. However, all post-baseline assessments will be used for PCS value determination and all assessments will be presented in the data listings.

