8.8 Safety Analyses

The Safety Set will be used to summarize safety data. Safety will be assessed for the following evaluations:

- Number, severity, seriousness, and causality of TEAEs
- Changes in vital signs ECGs, and clinical laboratory results (hematology, chemistry, and urinalysis) from baseline to post-baseline time points. Baseline is defined as the last non-missing assessment prior to the first dose.

Safety data, including TEAEs, 12-lead ECGs, vital signs (systolic and diastolic blood pressure, pulse rate, respiratory rate), and clinical laboratory data (biochemistry, hematology, and urinalysis), will be summarized with the descriptive statistics. Potentially clinically important findings will also be summarized or listed. The potentially clinically important values will be defined in the SAP.

Quantitative safety data as well as the difference from baseline, if applicable, will be summarized by descriptive statistics. Frequency counts will be compiled for classification of qualitative safety data. Direct safety comparisons between the two cohorts (the subjects of Japanese descent and Non-Hispanic Caucasian subjects) will be presented from the maribavir 400 mg dosing data. All other safety data from the 200 mg and 800 mg in the subjects of Japanese descent will be summarized and listed.

For each safety variable, the last value collected before the first dose of investigational product in that treatment period will be used as baseline for all analyses of that safety variable in that treatment period.

An AE (classified by preferred term [PT]) that occurred during the study will be considered a TEAE if it had a start date on or after the first dose of investigational product or if it had a start date before the date of the first dose of investigational product, but increased in intensity on or after the date of the first dose of investigational product. An AE that occurred after the follow-up phone call will not be counted as a TEAE.

Adverse events will be coded using the agreed-upon version of Medical Dictionary for Regulatory Activities, Version 23.0. or later. The number of events, incidence, and percentage of TEAEs will be calculated overall, by system organ class, and by PT. Treatment emergent adverse events will be further summarized by severity and relationship to investigational product. Adverse events related to investigational product, AEs leading to withdrawal, SAEs, and deaths will be similarly summarized/listed.

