### 2.2.2 Exploratory Pharmacokinetic Endpoints

### 2.2.3 Safety Endpoints

The safety analysis will be performed using the Safety Analysis Set. Safety endpoints include AEs, vital signs, ECG variables, and clinical laboratory variables. The following safety evaluations will be performed:

- Number, severity, seriousness, and causality of treatment-emergent adverse events (TEAEs).
- Changes in vital signs, ECGs, and clinical laboratory results (hematology, chemistry, and urinalysis) from baseline to post-baseline time points.

For each safety variable, the last value collected before the first dose of investigational product in that period will be used as baseline for all analyses of that safety variable in that period.

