## 7. SAFETY ANALYSIS

The safety analysis will be performed using the Safety Set. Safety variables include AEs, vital signs, ECG, and clinical laboratory variables. For each safety variable, the last value collected before the first dose of investigational product will be used as baseline for all analyses of that safety variable. Last Value on Treatment (LVOT) will be defined as the last valid assessment obtained after Baseline and until 7 days after last dose of investigational product.

All safety analyses will be conducted according to the treatment the subject actually received.

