### 7.2 Clinical Laboratory Data

Descriptive statistics for clinical laboratory values (in SI units) and changes from baseline at each assessment time point as well as shift tables from baseline to each visit for quantitative variables will be presented by cohort and treatment group for the following clinical laboratory variables (copy from the protocol).

**Hematology** Hemoglobin, hematocrit, red blood cells (RBC), platelet count, white blood cell count – total and differential (WBC), i.e. total neutrophils (absolute), eosinophils (absolute), monocytes (absolute), basophils(absolute), and lymphocytes (absolute).

**Biochemistry** Sodium, potassium, glucose(fasting), urea nitrogen, creatinine, calcium, chloride, thyroid stimulating hormone (TSH)a, thyroxine (free T4)triiodothyronine (T3), phosphate, protein, carbon dioxide, albumin, aspartate transaminase, alanine transaminase, gamma glutamyl transferase, alkaline phosphatase, total bilirubin, uric acid, and  $\beta$ -HCGa.

a Females only.

**Urinalysis** pH, glucose, protein, blood, ketones, bilirubin, nitrites, leukocyte esterase, and specific gravity.

Clinical laboratory test values are potentially clinically significant (PCS) if they meet either the low or high PCS criteria listed in [Table 1](#). The number and percentage of subjects with post-baseline PCS values will be tabulated by cohort and treatment group. The percentages will be calculated relative to the number of subjects with available baseline values and at least 1 post-baseline assessment. The numerator is the total number of subjects with at least 1 post-baseline

PCS value. A supportive listing of subjects with post-baseline PCS values will be provided including the subject number, baseline, and post-baseline values.

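### The rule for potentially clinically significant (PCS) values has no period window and rests on conflicting baselines, so Period 2 and 3 predose values can land in the wrong dose column

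*SAP*

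**What the plan says.** **Which values count.** SAP 12.2 leaves repeats at most post-baseline time points out of the summaries, then adds that "all post-baseline assessments will be used for PCS value determination". It gives no period and no end time.

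**Baseline.** The documents give two definitions.
- Study-wide: SAP 7 says "the last value collected before the first dose of investigational product will be used as baseline for all analyses of that safety variable". SAP 12.2 likewise takes the final assessment before IP starts, with no mention of period. Protocol 8.8 has "Baseline is defined as the last non-missing assessment prior to the first dose".
- Per period: SAP 2.2.3 says "For each safety variable, the last value collected before the first dose of investigational product in that period will be used as baseline". A later paragraph of Protocol 8.8 agrees: the last value before dosing "in that treatment period will be used as baseline for all analyses of that safety variable in that treatment period".

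**Layout and comparison.** SAP 7.2 states that "PCS values will be tabulated by cohort and treatment group"; SAP 7.3 and 7.4 use the same layout for vital signs and ECG. Protocol 8.8 says that direct safety comparisons between the cohorts "will be presented from the maribavir 400 mg dosing data".

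**Attribution to a dose.** SAP 7 says "All safety analyses will be conducted according to the treatment the subject actually received". SAP 7.1 assigns adverse events in washout to the preceding treatment, and SAP 5.5 has a similar rule for concomitant medications. There is no such rule for laboratory, vital sign or ECG values.

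**The concern.** Japanese subjects have laboratory tests, vital signs and an ECG before dosing in Periods 2 and 3. These values come after a dose of maribavir and before the next one. Whether they are post-baseline depends on which baseline wording the programmer follows, and if they are, no text says which dose column receives them.

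Caucasian subjects have a single period and leave the unit on Day 2; only a telephone call is scheduled after that. If the Period 2 predose value is counted under 400 mg, the Japanese cohort gets one more chance to be flagged in the comparison that Protocol 8.8 singles out. Its PCS percentage could then be higher with no drug or ethnic effect. If values are instead counted by visit, a finding made before the 200 mg or 800 mg dose appears in that dose's column.

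**Working it through.** **1. Check the look counts against the plan's own figure.** The schedules give laboratory samples at screening, at Day -1, and at predose and 24 h in each period.
- Japanese: 2 + 2 × 3 = 8
- Caucasian: 2 + 2 × 1 = 4

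Protocol Table 7 states 8 and 4 for both biochemistry and hematology, so the count agrees.

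**2. Count scheduled looks after 400 mg.** Protocol Tables 2 and 6 place post-dose laboratory tests at 24 h, and vital signs and ECG at 3 h and 24 h.

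| | Caucasian | Japanese, Period 1 post-dose only | Japanese, plus Period 2 predose |
|---|---|---|---|
| Laboratory tests | 1 | 1 | 2 |
| Vital signs, ECG | 2 | 2 | 3 |

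The Period 3 predose value follows 200 mg or 800 mg, so it adds nothing to 400 mg.

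**3. Apply each baseline wording.**
- *Study-wide.* Both later predose values are post-baseline. The Japanese cohort has 3 + 2 = 5 post-baseline laboratory looks and 6 + 2 = 8 for vital signs and ECG. Counted by visit, one of the two laboratory looks in each of the 200 mg and 800 mg columns precedes the dose. Counted by last dose taken, the Period 2 value goes to 400 mg and the Period 3 value to whichever dose was given in Period 2.
- *Per period.* A predose value is its own period's baseline and cannot count against the coming dose. But the Period 2 predose value still follows the Period 1 baseline and the 400 mg dose, and no sentence closes Period 1 for PCS. It may be counted under 400 mg or not counted at all.

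The choice of baseline therefore does not settle the matter. Several criteria in SAP Tables 1 and 3 also use the observed value alone (for example fasting glucose, chloride, neutrophils, lymphocytes, urinalysis and QRS), so the baseline does not change which values meet them.

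**4. How close the extra look is to drug-free.** Protocol 1.2.3 gives a half-life of about 5 to 7 h. Over 72 h that is 72/7 = 10.3 to 72/5 = 14.4 half-lives, leaving at most 2^(-10.3), or about 0.08%.

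**5. Illustrate the size.** Let p be the chance that one look is flagged. The documents give no value, so p is an assumption, shown over a range. With k independent looks, a subject is flagged with probability 1 − (1 − p)^k, and the expected number among 12 is 12 times that. For laboratory tests at p = 5%: 12 × 0.05 = 0.60 with one look, and 12 × (1 − 0.95²) = 12 × 0.0975 = 1.17 with two.

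| p | Labs, Caucasian (k = 1) | Labs, Japanese (k = 2) | Vital signs/ECG, Caucasian (k = 2) | Vital signs/ECG, Japanese (k = 3) |
|---|---|---|---|---|
| 1% | 0.12 | 0.24 | 0.24 | 0.36 |
| 5% | 0.60 | 1.17 | 1.17 | 1.71 |
| 10% | 1.20 | 2.28 | 2.28 | 3.25 |
| 20% | 2.40 | 4.32 | 4.32 | 5.86 |

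If a subject's looks agree completely, the extra look adds nothing.

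**6. Effect of a window.** With only post-dose values through 24 h, the looks at 400 mg are 1 against 1 and 2 against 2.

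**The case against.** The strongest defence is that the plan already works by period. SAP 2.2.3 and the later paragraph of Protocol 8.8 tie both baseline and analysis to the period, and Protocol 3.1 describes safety evaluation from Day 1 predose to 24 h after dosing in each period. On that view Period 1 ends at 24 h in both cohorts. The SAP 12.2 sentence is mainly there to keep repeats and unscheduled values in PCS. SAP 1 places table specifications in a separate document, which may contain a window.

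Part of this stands. A reader might infer that a predose value must be misplaced one way or the other. The documents do not force that: per period, it cannot count against the coming dose and may enter no PCS count. A reader might also take both later predose values as extra looks at 400 mg; only the Period 2 value can be.

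The rest does not clear the point. SAP 7 and 12.2 use the study-wide wording, and 12.2 is the section that sets the PCS rule. Protocol 3.1 describes when assessments are made and includes the predose assessment in each period; it does not say when a dose's PCS window closes. A window in an unseen specification would not remove the conflict between SAP sections.

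The objection to the size is fair. No flag rate is documented, many criteria also require a change from baseline, and a subject with a stable level outside an observed-value limit would be flagged at every look.

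**Conclusion.** The point holds in a limited form. The baseline definitions conflict within the SAP and within Protocol 8.8. Under the study-wide wording, the PCS rule brings Period 2 and 3 predose values into the dose tables without saying where they belong. Under the per-period wording, the Period 2 predose value can still become an extra look at Japanese 400 mg: 2 against 1 for laboratory tests, 3 against 2 for vital signs and ECG.

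The look counts come from the schedules. The inflation does not: 1.17 against 0.60 of 12 rests on an assumed 5% per look and on independence, and is an upper bound when a subject's looks are positively correlated. A reader might infer that the Japanese PCS percentage will be inflated; the documents show only that the text permits it.

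The consequence is confined to descriptive safety tables with 12 subjects per cohort, no test and no decision rule, and the listings show all assessments. The PK analyses are unaffected. It is worth correcting because the affected column is the one used to compare the cohorts.

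**What to change.** Amend the SAP as follows.
1. Use the per-period baseline of SAP 2.2.3 in SAP 7 and 12.2, and note in SAP 14 which of the two Protocol 8.8 wordings is followed.
2. State in SAP 12.2 that PCS for each dose uses assessments, including repeats and unscheduled ones, taken after that dose and before the next period's predose assessments.
3. State that Period 2 and 3 predose values serve only as the baseline of their own period.
4. Base the Japanese versus Caucasian PCS comparison at 400 mg on assessments through 24 h in both cohorts.

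Item 2 keeps the repeats and unscheduled values that SAP 12.2 means to retain. Item 4 makes scheduled looks equal. A later unscheduled Japanese value could then appear in the 400 mg dose table but not in the cohort comparison, so a footnote should say so.

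The cost is a few sentences of SAP text and matching programming. The downside is that an abnormality first seen at the next period's predose check will appear in the listings, and as an adverse event if clinically significant, but not in the PCS table.
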